7.2 Handling of Safety Parameters

7.2.1 Reporting of Adverse Events

All adverse events (related and unrelated) grade 1-5 occurring during the study and up to 30 days after the last dose of study medication must be reported and recorded in the study database. Reporting the specific time of onset of a given AE is only necessary when it occurs in relation to study drug administration.

7.2.2 Reporting of Serious Adverse Events (immediately reportable)

Any clinical adverse event or abnormal laboratory test value that is *serious* and which occurs during the course of the study (as defined in section 7.1.3below), must be reported to SARC **within** *24 hours* of the site investigator becoming aware of the event. If only limited information is initially available, follow-up reports are required. The original SAE form must be kept on file at the study site.

SAEs must be reported on the MedWatch Form 3500A along with the completed Fax/Email Coversheet and faxed or emailed to SARC office (See Appendix B). SARC will notify Merck within 1 working day by faxing the complete report to:

Merck Global Safety Attn: Worldwide Product Safety [contact]

Related Serious Adverse Events *MUST* be collected and reported regardless of the time elapsed from the last study drug administration, even if the study has been closed.

Unrelated Serious Adverse Events must be collected and reported during the study and for up to 30 days after the last dose of study medication

7.2.3 Reporting of Overdose to the Sponsor and to Merck

If an adverse event(s) is associated with ("results from") the overdose of pembrolizumab, the adverse event(s) is reported as a serious adverse event, even if no other seriousness criteria are met.

If a dose of pembrolizumab meeting the protocol definition of overdose is taken without any associated clinical symptoms or abnormal laboratory results, the overdose is reported as a non-serious Event of Clinical Interest (ECI), using the terminology "accidental or intentional overdose without adverse effect."

All reports of overdose with and without an adverse event must be reported **within 24 hours** to SARC. SARC will notify Merck within 1 working day as outlined in the section 7.2.2.

7.2.4 Reporting of Pregnancy and Lactation to the Sponsor and to Merck

Although pregnancy and lactation are not considered adverse events, it is the responsibility of the site investigators or their designees to report any pregnancy or lactation in a patient (spontaneously reported to them), including the pregnancy of a male patient's female partner that occurs during the trial or within 120 days of completing the trial completing the trial, or 30 days following cessation of treatment if the patient initiates new anticancer therapy, whichever is earlier. All patients and female partners of male patients who become pregnant must be followed to the completion/termination of the pregnancy. Pregnancy outcomes of spontaneous abortion, missed abortion, benign hydatidiform mole, blighted ovum, fetal death, intrauterine death, miscarriage and stillbirth must be reported as serious events ((Important Medical Events). If the pregnancy continues to term, the outcome (health of infant) must also be reported.

Such events must be reported **within 24 hours** to SARC. SARC will notify Merck within 1 working day as outlined in the section 7.2.2.

7.2.5 Reporting of Serious Adverse Events

Any serious adverse event, or follow up to a serious adverse event, including death due to any cause other than progression of the cancer that occurs to any patient from the start of study treatment (Day 1) through 30 days following cessation of treatment, or the initiation of new anti-cancer therapy, whichever is earlier, whether or not related to pembrolizumab, must be reported **within 24 hours** to SARC. SARC will notify Merck within 1 working day as outlined in the section 7.2.2.

Non-serious Events of Clinical Interest will be forwarded to Merck Global Safety and will be handled in the same manner as SAEs.

Additionally, any serious adverse event assessed by a site Investigator, who is a qualified physician as related to pembrolizumab, regardless of the time elapsed, even if the study has been closed, should be reported to SARC and Merck (as outlined in the section 7.2.2).

A copy of all 15 Day Reports and Annual Progress Reports will be submitted as required by FDA and will be cross referenced according to local regulations to Merck's Pembrolizumab IND Number at the time of submission

A copy of all reports submitted to FDA will be sent to Merck at: Merck Global Safety, Attn: Worldwide Product Safety; [contact]

All subjects with serious adverse events must be followed up for outcome.

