5.6.1 Duration of Participation

Each patient will participate in the trial from the time of Informed Consent Form (ICF) is signed through final protocol-specified contact. After a screening phase for eligibility, patients will receive pembrolizumab every 3 weeks. Treatment for patients that achieve SD, a PR, or a CR can continue for a maximum of 2 years. At the discretion of the investigator, patients who have progressive disease (PD) but continue to achieve clinical benefit, may also continue on therapy for a maximum total duration of treatment of *35cycles*.

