7.1.3 Serious Adverse Events

A serious adverse event is any adverse event occurring at any dose or during any use of pembrolizumab that:

- Results in death;
- Is life threatening;
- Results in persistent or significant disability/incapacity;
- Results in or prolongs an existing inpatient hospitalization;
- Is a congenital anomaly/birth defect;
- Is a new cancer (that is not a condition of the study);
- Is associated with an overdose;
- Is another important medical event

Progression of the disease under study is not considered an adverse event unless it results in hospitalization or death.

Any serious adverse event, or follow up to a serious adverse event, including death due to any cause other than progression of the cancer that occurs to any patient from the time treatment is started (Day 1) through 30 days following cessation of treatment, or the initiation of new anti-cancer therapy, whichever is earlier, whether or not related to pembrolizumab, must be reported within 24

hours to the SARC. SARC will notify Merck within 1 working day as outlined in the section 7.2.2.

Non-serious Events of Clinical Interest will be handled in the same manner as SAEs.

Additionally, any serious adverse event assessed by a site Investigator as related to pembrolizumab, regardless of the time elapsed, even if the study has been closed, should be reported to SARC and Merck (as outlined in the section 7.2.2).

A copy of all reports submitted to FDA will be sent to Merck at: Merck Global Safety, Attn: Worldwide Product Safety; [contact]

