9.1.3 Biopsy

Pre- and post-treatment biopsies will be required for 20 patients in each of the expansion cohorts of UPS and LPS. Mandatory biopsies will be obtained during screening prior to first study drug administration (week 0), and at week 8 (\pm 1 week). Additional optional biopsies of easily accessible tumors may also be performed at cycle 12 (week 34) and at time of progression. Surgical excisional or core biopsies are acceptable. Ten patients whose disease is not amenable to biopsy can be enrolled in each of the expansion cohorts of UPS and LPS and no biopsy will be required.

| | Schedule for Tumor Bio | psy Samples Colle | ction |
|----------------------------------|--|--|--|
| Time points f | or Tumor biopsy samples collection | 20 Patient Cohorts (UPS and LPS) | 10 Patient Cohorts (UPS and LPS) without disease amenable to |
| Archival Tumor Samples | After eligibility is confirmed | Mandatory | Mandatory |
| Mandatory , pre- treatment | After eligibility is confirmed, prior to first study drug administration | Mandatory | |
| Mandatory, on- treatment | At week 8 (+/- 1week) | Mandatory | |
| Optional, cycle 12 | At week 34 (+/- 1week) | Optional | |
| Optional, end of study treatment | At disease progression | Optional | |

Archival tissue will be mandatory for PD-L1 testing on all patients.

Biopsies will be processed for IHC:

1. Evaluation of PD-L1 expression

2. Evaluation of CD8⁺ and CD4⁺ T cell infiltrates.

Biopsies will be processed for single cell suspensions for intracellular cytokine assays:

1. Expression of inhibitory receptors including Tim-3 and BTLA by $\rm CD8^+$ and $\rm CD4^+\,TILs.$

2. Expression of a number of inhibitory ligands including PD-L1, HVEM, and galectin-9 by tumor cells and tumor-infiltrating antigen presenting cells.

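### The start of AE/SAE reporting is inconsistent: under the explicit Day 1 rule, a serious complication of the mandatory screening biopsy before the first dose need not be reported within 24 hours

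*Combined protocol and SAP*

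**What the plan says.** All references are to the combined protocol and SAP.

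**Places that point to Day 1**
- Section 7.2.5 requires SAEs to reach the coordinating sponsor within 24 hours if they occur "from the start of study treatment (Day 1) through 30 days following cessation of treatment", or until new anti-cancer therapy if that is earlier.
- Section 7.1.3 states the same window: "from the time treatment is started (Day 1) through 30 days following cessation of treatment". Its definition opens: "A serious adverse event is any adverse event occurring at any dose or during any use of pembrolizumab".
- The adverse event row of the study calendar (section 10) is blank in the pre-study column. Section 10.1 lists the tumor biopsy among screening procedures but no recording of adverse events. That recording first appears in section 10.2, for the treatment period.
- Section 11.1.1 makes patients evaluable for toxicity from their first pembrolizumab treatment.

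**Places that point to an earlier start**
- Section 7.2.1: "All adverse events (related and unrelated) grade 1-5 occurring during the study and up to 30 days after the last dose".
- Section 7.2.2, on unrelated events: "Unrelated Serious Adverse Events must be collected and reported during the study and for up to 30 days after the last dose of study medication".
- Section 5.6.1: "Each patient will participate in the trial from the time of Informed Consent Form (ICF) is signed".

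**The procedure at issue**
- Section 9.1.3: "Mandatory biopsies will be obtained during screening prior to first study drug administration (week 0". In the expansion this applies to 20 patients in each of the two cohorts. Section 2.17 shows that it also applied to the initial enrollment.

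**The concern.** The screening biopsy is an invasive procedure done for the correlative studies, and the protocol requires it before any drug is given. If it causes a serious complication before the first dose, the only two sections that give SAE reporting an explicit start date place the event outside the window. The event also does not fit an SAE definition that presupposes use of the drug. A complication that stops the patient from being dosed at all is the clearest case, because no Day 1 ever occurs.

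What is at stake is safety oversight. Section 12.1.2 has the Clinical Trials Review Committee review the SAEs that are reported to it. A site that applies the Day 1 rule literally would send nothing, so the committee might not learn of harm from a procedure that patients undergo for research. A site that reads the protocol from consent onward would report the same event. Sites could therefore differ, and the final report could not say with confidence how often the mandated biopsy caused serious harm.

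**Working it through.** The plan gives no figure on this point, so there is none to reproduce. The check is a comparison of passages, followed by a sense of scale.

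**Step 1. When does each provision start?**

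| Place | Stated or implied start | Would it capture a serious biopsy complication before dosing? |
|---|---|---|
| 7.1.3, reporting window | Day 1 of treatment | No |
| 7.1.3, SAE definition | Use of pembrolizumab | No |
| 7.2.5 | Day 1 of treatment | No |
| 10.1, 10.2 and calendar | Treatment period | No |
| 7.2.1 | During the study, no start given | Yes, if the study starts at consent; but the section sets no 24-hour limit |
| 7.2.2, last sentence | During the study, no start given | Yes, if the study starts at consent |
| 5.6.1 | Consent (participation) | Supports the earlier start, but is not a reporting rule |

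**Step 2. Does section 7.2.2 settle it?** Its first sentence covers a serious event "which occurs during the course of the study (as defined in section 7.1.3below". The cross-reference can be read as defining the period or as defining what counts as serious. If it defines the period, it leads to the Day 1 window in 7.1.3. If it defines seriousness, it leads to the drug-tied definition in 7.1.3. Neither reading states that reporting starts at consent.

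**Step 3. Which interval is affected?** Only the time from the week 0 biopsy to the first dose, within a screening period of up to 30 days (section 10.1). The week 8 biopsy is taken on treatment and lies inside the Day 1 window. So does an event with onset on or after Day 1, even if the screening biopsy caused it.

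**Step 4. Scale.** Mandated screening biopsies in the expansion: 2 × 20 = 40 (section 9.1.3). The documents give no rate of serious biopsy complications, so the rate r is an assumption shown over a range. Assuming independent patients, the chance that at least one serious complication occurs is 1 − (1 − r)^40.

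| Assumed r | Calculation | Chance of at least one | Expected number, 40r |
|---|---|---|---|
| 0.1% | 1 − 0.999^40 | 3.9% | 0.04 |
| 1% | 1 − 0.99^40 | 33.1% | 0.4 |
| 2% | 1 − 0.98^40 | 55.4% | 0.8 |
| 5% | 1 − 0.95^40 | 87.1% | 2.0 |

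These are chances that an event occurs. To be missed, the event must also begin before Day 1, and the site must follow the Day 1 rule.

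**The case against.** The strongest case on the other side has four parts.

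1. *The event may already be reportable.* A reader might infer that pre-dose biopsy complications simply fall outside the reporting rules. The documents do not support that. Sections 7.2.1 and 7.2.2 cover related and unrelated events during the study, and participation starts at consent. On that reading a serious biopsy complication has to be reported. This stands, and it makes the finding an inconsistency rather than a plain exclusion. It does not remove the finding, because the sections that do state a start date both state Day 1, and the screening list and calendar agree with them.

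2. *Counting toxicity from first dose is proper.* A reader might see section 11.1.1 as part of the defect. It is not. The safety objective in section 1.2 concerns pembrolizumab, and a toxicity population that starts at first dose fits it. This stands in full.

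3. *The event need not be hidden.* The committee's remit in section 12.1.2 is not limited to SAEs, section 12.2 provides biweekly calls with sites, and section 5.8 requires the reason for study removal to be documented. An event could come to light by these routes. That stands, so the right wording is that it might not reach the committee. None of these routes has the 24-hour limit of SAE reporting.

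4. *Other instructions may exist.* The Operations Manual and the consent pages are not available here and might address procedure-related events. They could help sites in practice, but the conflict within the protocol would remain.

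**Conclusion.** The start of AE and SAE reporting is inconsistent across sections 5.6.1, 7.1.3, 7.2.1, 7.2.2, 7.2.5 and the study calendar. Under the explicit Day 1 rule, a serious complication of the mandatory week 0 biopsy with onset before the first dose would not have to be reported within 24 hours.

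The point is narrow. It concerns one procedure and one interval, and it does not affect ORR, the success rule of 8 responses in 40, or the stated error rates. The figures of 4% to 87% rest on assumed complication rates and on independence between patients. It would be wrong to read them as chances of an unreported event.

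The point still merits a change, because a stated rule, and not mere silence, leaves these events out, and because the biopsy is a research requirement.

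**What to change.** - In 7.1.3 and 7.2.5, add that SAEs related to a protocol-mandated procedure, including the screening biopsy, are reported within 24 hours from signature of consent.
- In 7.1.3, extend the SAE definition so that it covers mandated study procedures as well as use of pembrolizumab.
- In 7.2.1 and 7.2.2, state the same start in place of the undefined reference to the study, and make clear what the cross-reference to 7.1.3 defines.
- In section 10.1 and the study calendar, add adverse event recording before treatment.
- Leave the toxicity population in 11.1.1 as first dose onward, and tabulate pre-dose procedure-related events separately so that drug toxicity rates are not diluted or inflated.

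The cost is a set of small edits in several sections, one additional table, and possibly a few more SAE reports. No sample size, endpoint or analysis of response changes.

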8. PHARMACEUTICAL INFORMATION

8.1 Study Agent

Pembrolizumab is a potent and highly selective humanized mAb of the IgG4/kappa isotype designed to directly block the interaction between PD-1 and its ligands, PD-L1 and PD-L2.

8.2 Preparation and Administration

Pembrolizumab will be given at 200 mg intravenously every 3 weeks.

8.3 Formulation, Packaging and Labelling

Clinical supplies will be affixed with a clinical label in accordance with regulatory requirements. Pharmacist will receive open label packages of the drug. Clinical Supplies will be provided by Merck as summarized in Table 7.

Table 7. Product Descriptions

| Product Name & Potency | Dosage Form |
|--------------------------|------------------------|
| Pembrolizumab 100 mg/4ml | Solution for Injection |

8.4 Storage and Handling Requirement

Clinical supplies must be stored in a secure, limited-access location under the storage conditions specified on the label. Receipt and dispensing of trial medication must be recorded by an authorized person at the trial site. Clinical supplies may not be used for any purpose other than that stated in the protocol.

8.5 Agent Ordering

Pembrolizumab will be provided by Merck. Details will be provided in the Operations Manual.

8.6 Agent Accountability

Accountability and patient compliance will be assessed by maintaining adequate drug dispensing and return records. Compliance with individual patient dosing is assured as the drug is administered intravenously and recorded at the clinical site.

Accurate records must be kept for each study drug provided by Merck. The drug dispensing log must be kept current and contain the following information:

- documentation of drug shipments received from Merck (date received and quantity)
- disposition of unused study drug not dispensed to patient
- the identification of the patient to whom the study medication was dispensed
- the date(s) and quantity of the study medication dispensed to the patient

This inventory must be available for monitoring. All supplies, including unused, partially used or empty containers will be destroyed according to sites drug destruction policy. Copies of the dispensing & inventory logs will be sent to SARC for remote monitoring.

8.7 Destruction of Pembrolizumab

Local or institutional regulations may require immediate destruction of used pembrolizumab for safety reasons e.g., cytotoxicity. In these cases, it may be acceptable for investigational site staff to destroy dispensed pembrolizumab before monitoring is done provided that source document verification is performed on the remaining inventory and reconciled against the documentation of quantity shipped, dispensed, returned and destroyed.

Written documentation of destruction must contain the following:

- Identity (batch numbers or patient numbers) of pembrolizumab destroyed
- Quantity of pembrolizumab destroyed
- Date of destruction (date discarded in designated hazardous container for destruction)
- Method of destruction (the site must provide the sponsor with documentation of their institutional policy and procedures for handling and disposing of hazardous drugs)
- Name and signature of responsible person (or company) who destroyed pembrolizumab.

A list of the adverse events and potential risks associated with pembrolizumab can be found in Section 7.1.

9. CORRELATIVE/SPECIAL STUDIES

9.1 Laboratory Correlative Studies

All biospecimens collected from patients enrolled in SARC028 study will be kept at a SARC designated specimen bank

9.1.1 Collection, Handling and Shipping of Specimens

Details for collection, handling and shipment of specimens will be provided in the Operations Manual.

9.1.2 Correlative Studies

The following correlative studies will be performed using blood for research studies and tumor tissues collected from the patients included in the study. In the expansion cohort, correlative tumor samples will be collected from 20 patients in each of the expansion cohorts of UPS and LPS. Ten (10) patients in each expansion cohort whose disease is not amenable to biopsy can be enrolled and for these patients, tissue correlative samples will not be collected.

All subjects enrolled will have correlative blood samples collected.

• Evidence of immune up-regulation at tumor sites:

 $_{\odot}$ $_{}$ Increased tumor-infiltrating CD8+ T cells using immunohistochemistry (IHC).

• Evaluation of PD-1and PD-L1 expression by T cells and malignant cells, respectively, using IHC.

Sections of formalin-fixed, paraffin-embedded tumor samples will be obtained from tumor biopsies of the patients as previously indicated. Standard immunohistochemistry (IHC) will be performed using antibodies against human B7-H1/PD-L1, human PD-1, CD3, CD8, CD4 and may include additional markers: CCR7, CD45RO, CD68 and CSPG4. Slides will be evaluated and scored independently by two experienced pathologists. PD-L1 expression will be expressed as % of positive cells among malignant cells. PD-1 expression will be expressed as % of PD-1 positive cells relative to the total number of CD3 cells. We expect to observe a significant increase of CD8⁺ TILs after treatment with pembrolizumab as compared to pre-treatment. We also expect that PD-L1 expression by malignant cells will increase after treatment with pembrolizumab as compared to pre-treatment.

• Inhibition of malignant cell proliferation, increased pro-apoptotic activity, upregulation of HLA antigen and MA expression, and inhibition of STAT signaling pathways associated with sarcoma cell proliferation and survival:

 $_{\odot}$ The expression of β2m-associated HLA-A and HLA-B/C loci gene products and of HLA class II antigens will be assessed by immunostaining of frozen tissue sections. The HLA-A-specific mAb LGIII-147.4.1[46], the HLA-B/C-specific mAb B1.23.2 [47] and the HLA class II antigen-specific mAb LGII-612.14 [48] will be used as molecular probes.

• The expression of APM components LMP2, LMP7, LMP10, TAP1, TAP2, calnexin, calreticulin, ERP57 and tapasin will be assessed by staining formalin fixed, paraffin embedded tissue sections with the mAb SY-1, HB2, TO-7, NOB1, NOB2, TO-5, TO-11, TO-2 and TO-3 [49, 50].

• To investigate the effect of therapy on sarcoma cell proliferation and apoptosis, sections of formalin fixed, paraffin embedded sarcoma metastases will be analyzed for p-Histone H3 and Cleaved Caspase-3 expression by IHC staining. The results will be expressed as the positive cell numbers from 10 randomly selected high-power (magnification ×200) fields per section by quantitative analysis.

• Other immunological endpoints will include studies of STAT 1/3/5a/5b and IFNAR, MHC class I and pERK expression.

 Reversal of PD1⁺ TA-specific CD8⁺ and CD4⁺ T cell dysfunction and rescue of memory TA-specific CD8⁺ and CD4⁺ T cells from terminal exhaustion: Tumor biopsy samples will be processed to obtain single cell suspensions to isolate TILs and tumor cells. Multiparameter flow cytometry will be used to investigate the phenotype and functions of TILs and the expression of PD-L1 by sarcoma cells and tumor-infiltrating cells ex vivo. CD3⁺ T cells will be isolated with magnetic beads (Miltenyi, Biotec) and CD3⁺ and non-CD3⁺ cells will be used for flow cytometry studies. We expect that therapy with pembrolizumab will result in increased number and function of CD8⁺ and CD4⁺ TILs at tumor sites.

Evaluation of NY-ESO-1-specific CD8⁺ and CD4⁺ T cells in patients with NY-ESO-1 expressing sarcoma at periphery (leukapheresis) and at tumor sites using flow cytometry including tetramer and intracellular cytokine staining. CD8+ and CD4+ T cell responses against NY-ESO-1 and other sarcoma antigens will be evaluated from PBLs of the sarcoma patients using peptide libraries and flow cytometry assay.

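### Section 9.1.2 reports p-Histone H3 and Cleaved Caspase-3 as counts with no malignant-cell denominator, so a change in tumor cellularity alone can shift this exploratory readout

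*Combined protocol and SAP*

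**What the plan says.** The aim in section 9.1.2 is "To investigate the effect of therapy on sarcoma cell proliferation and apoptosis". Sections of fixed, embedded tumor "will be analyzed for p-Histone H3 and Cleaved Caspase-3 expression by IHC staining". The scale is then fixed: "The results will be expressed as the positive cell numbers from 10 randomly selected high-power" fields at ×200 in each section. The text does not say which cells count as positive cells. It gives no total to divide by and no adjustment for how much tumor the fields contain.

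Two other readouts in section 9.1.2 do have denominators: "PD-L1 expression will be expressed as % of positive cells among malignant cells", and "PD-1 expression will be expressed as % of PD-1 positive cells relative to the total number of CD3 cells".

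The section also predicts that tissue composition will change. For immunohistochemistry: "We expect to observe a significant increase of CD8"-positive infiltrating lymphocytes compared with baseline. For flow cytometry, therapy "will result in increased number and function of CD8"-positive and CD4-positive infiltrating cells. Section 9.1.3 gives the paired time points: "Mandatory biopsies will be obtained during screening prior to first study drug administration (week 0), and at week 8". Later biopsies are optional.

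Section 13.3 does not mention these two markers and treats the correlative work as exploratory. Section 9.1.1 refers only specimen collection, handling and shipment to the Operations Manual, not scoring.

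**The concern.** The question is about a rate in malignant cells: what share of them is dividing or dying. A count over a fixed number of fields is that rate multiplied by the number of malignant cells in the fields, plus any positive non-malignant cells that are counted. The plan expects the mix of cells to change between week 0 and week 8, so the count and the rate can separate.

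Random choice of fields does not help. It protects against selective reading within a section, not against a systematic difference in composition between two sections from the same patient.

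At stake is interpretation. A fall in p-Histone H3-positive cells could be read as inhibited proliferation when the fields simply contain fewer tumor cells. A real rise in the apoptotic fraction could be diluted in the same way.

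**Working it through.** The plan gives no sample size, effect size or test for this readout, so there is no figure of its own to reproduce. The check asks how far the count can move when nothing changes in the malignant cells. Every rate and share below is an assumption; none is in the documents.

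**1. Displacement model.** Fields hold N malignant cells at baseline, with a share p positive. On treatment, infiltrating cells replace a fraction d of them one for one, p stays the same, and infiltrating cells are positive at rate q.

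- Count before: N·p
- Count after: N·(1−d)·p + N·d·q
- Ratio after/before: (1−d) + d·q/p
- Percentage of malignant cells positive, after: N·(1−d)·p ÷ N·(1−d) = p, unchanged

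| d | q = 0, or infiltrate not counted | q = p | q = 2p |
|---|---|---|---|
| 20% | 0.8 (−20%) | 1.0 (0%) | 0.8 + 0.4 = 1.2 (+20%) |
| 60% | 0.4 (−60%) | 1.0 (0%) | 0.4 + 1.2 = 1.6 (+60%) |

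The true change in the malignant-cell fraction is zero in every cell of the table.

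**2. Allowing for infiltrate at baseline.** Let C = 10,000 cells in the fields at both biopsies, with p = 2%. The infiltrating share g rises from 5% to 20%, from 5% to 40%, or from 10% to 50%. Count = C·[(1−g)·p + g·q].

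| Cells counted | 5% to 20% | 5% to 40% | 10% to 50% |
|---|---|---|---|
| All positives, q = 1% | 195 to 180 (−7.7%) | 195 to 160 (−17.9%) | 190 to 150 (−21.1%) |
| All positives, q = 2% | 200 to 200 (0%) | 200 to 200 (0%) | 200 to 200 (0%) |
| All positives, q = 4% | 210 to 240 (+14.3%) | 210 to 280 (+33.3%) | 220 to 300 (+36.4%) |
| Malignant positives only | 190 to 160 (−15.8%) | 190 to 120 (−36.8%) | 180 to 100 (−44.4%) |

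The last row matters most. Even if readers exclude every lymphocyte, the count still falls because fewer malignant cells are in view.

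**3. A true effect can be diluted.** Suppose the apoptotic fraction of malignant cells rises 1.5-fold and only malignant positives are counted. The observed ratio is 1.5·(1−g₁)/(1−g₀):

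- 1.5 × 0.80/0.95 = 1.26
- 1.5 × 0.60/0.95 = 0.95
- 1.5 × 0.50/0.90 = 0.83

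In two of the three scenarios a real increase reads as a decrease.

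**The case against.** **Which cells are counted is not stated.** A reader might infer that lymphocytes are included. The documents do not establish this. The aim names sarcoma cells, and PD-L1 scoring in the same section already requires readers to pick out malignant cells. If infiltrating cells are excluded, the upward shifts disappear. The downward shift from fewer malignant cells per field remains.

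**A count per area is a legitimate quantity.** Fewer dividing tumor cells in a given area, because tumor cells have gone, can itself be a treatment effect, and a percentage of surviving cells does not show it. This stands. The count should be kept, but it does not isolate a change in the fraction that is dividing or dying.

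**Field choice.** It is tempting to restrict counting to viable-tumor fields. In an open-label trial (section 5.3), that would replace random fields with reader-chosen ones and add selection, so it is not recommended here.

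**Size.** A reader might take 20-60% as an estimate of bias. It is not: d, p and q are all assumed, and the shift is zero when q = p or when cellularity does not change. Nor do the documents show that the shift would be largest in responding tumors.

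**Weight.** No objective in section 1 names proliferation or apoptosis. Section 13.3 sets no test for them, and the immunohistochemistry list in section 9.1.3 omits them. The comparison of week 0 with week 8 for these markers is a fair inference from the aim and the biopsy schedule, not a written analysis. Planned CD3, CD4 and CD8 staining would let a reader see a change in infiltrate beside the counts, which makes misreading less likely. It does not supply a malignant-cell total.

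**Conclusion.** The point holds as a cheap improvement to an exploratory readout. The stated target is a property of sarcoma cells, the reported number has no malignant-cell denominator, and the plan itself predicts a change in tissue composition. A shift in tumor cellularity can therefore move the count with no change in the proliferating or apoptotic fraction. The direction is downward when cellularity falls and only malignant positives are counted; it can be either way if infiltrating cells are counted too.

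The size is unknown. The 20-60% figures rest on one-for-one displacement of 20-60% of malignant cells, on no infiltrate at baseline, and on positivity of infiltrating cells at zero or at twice the malignant-cell rate. The second set of assumptions, with infiltrate already present at baseline, gives −21% to +36% counting all positives and −16% to −44% counting malignant positives only.

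A reader might go further and infer that the trial's conclusions are biased. The documents do not support that: the ORR rule, PFS, OS and safety do not use these markers.

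**What to change.** In section 9.1.2:

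- Keep the 10 randomly selected fields.
- State that positive malignant cells are the cells counted.
- Count all malignant cells in the same fields. Report the percentage positive, as already done for PD-L1, as the measure of effect on sarcoma cells.
- Report the per-field count beside it, labelled as a density.
- Compare the two biopsies within patient, and report how many sections contain no malignant cells.

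The cost is counting time on slides already planned, with no new tissue or procedure. This assumes readers can separate malignant from infiltrating cells on these slides, as PD-L1 scoring requires. If they cannot, a tumor or lymphoid co-stain would be needed and the cost would be higher.

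The downside is that a section without malignant cells yields no percentage. Such sections may be more common in responders, so the loss may be informative. Keeping the count for those sections, and reporting their number, means no information now planned is given up.
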